## 7 DERIVED AND COMPUTED VARIABLES

Mean change from baseline (baseline is defined in Section 12.1.4 “Definitions for Statistical Data Analysis”) is the mean of all individual subjects’ change from baseline values. Each individual change from baseline will be calculated by subtracting the individual subject’s baseline value from the value at the timepoint. The individual subject’s change from baseline values will be used to calculate the mean change from baseline.

Mean percent change from baseline is the mean of all individual subjects’ percent change from baseline values. Each percent change from baseline will be calculated by subtracting the individual subject’s baseline value from the value at the desired timepoint and then dividing this calculated value by the individual subject’s baseline value and multiplying by 100. These individual subjects’ percent changes from baseline values will be used to calculate the mean percent change from baseline.

When the baseline value is 0, 1 will be used in the denominator for calculating the percent change from baseline.

The QT interval corrected using Bazett’s formula (QTcB) will be calculated as follows:

$$QTcB = \frac{QT}{\sqrt[2]{\frac{60}{HR}}}$$

The QT interval corrected using Fridericia’s formula (QTcF) will be calculated as follows:

$$QTcF = \frac{QT}{\sqrt[3]{\frac{60}{HR}}}$$

Reported BMI will be calculated at site from the body weight and height using the following formula:

$$BMI = \frac{\text{weight in kilograms}}{\text{height in meters}^2} \quad (\text{kg/m}^2)$$

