### 7.3.2 Fagerström Test for Nicotine Dependence (FTND)

The FTND will be used in its revised version (**Heatherton et al 1991**), as updated in 2012 (**Fagerström et al. 2012**). These questions are to be answered by the subject themselves. It is conducted at Screening to determine subject's dependence on nicotine and on the Day 90 Visit to assess any changes in their dependence on nicotine.

**Table 4** describes the six questions the questionnaire consists of, and the scores associated with each question.

The FTND total score will be derived by summing the individual item scores if all items are non-missing, otherwise the total score will be set to missing. For the FTND total score, descriptive statistics and frequency tables according to the following classification will be provided (**Fagerström et al. 2012**):

Mild	0 – 3
Moderate	4 – 6
Severe	7 – 10

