**Table 4: Scoring for the Fagerstrom Test for Nicotine Dependence**

FTND Question	Response	Score
2 Do you find it difficult to refrain from smoking in places where it is forbidden?	Yes	1
	No	0
3 Which cigarette would you hate most to give up?	The first one in the morning	1
	Any other	0
	10 or less (up to ½ pack)	0
4 How many cigarettes per day do you typically smoke?	11 to 20 (a little more than ½ pack, up to a full pack)	1
	21 to 30 (a little more than a pack, up to 1½ packs)	2
	31 or more (more than 1½ packs)	3
5 Do you smoke more frequently during the first hours after waking than during the rest of the day?	Yes	1
	No	0
6 Do you smoke if you are so ill that you are in bed most of the day?	Yes	1
	No	0

If the baseline score is 0, the percent change from baseline will be calculated using a value of 1 for the denominator.

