### 7.3.5 Minnesota Nicotine Withdrawal Scale (revised edition) Questionnaire

The MNWS (**Hughes and Hatsukami 2008**) is a 24 hour recall that will be completed by the subject him/herself daily from Day 0 to Day 6, and on the second day of every visit during the ambulatory period. From Day 0 to Day 6 only, MNWS questionnaire must be asked prior to start of product use/smoking and no later than 10:00 AM. On Day 31 and Day 61 the assessment of MNWS will be conducted irrespective of the time of product use but no later than 10:00 AM. Whilst on Day 91 the assessment of MNWS has to be conducted prior to smoking but no later than 10:00 AM.

The self-reported part of the MNWS consists of the following 15 items which are rated over the last 24 hours on a scale of 0 to 4 (see **Table 7**). Higher scores indicate greater intensity on that scale.

The total scores will be derived by calculating the average of all the non-missing data from the first 9 items. If more than 50% of the first 9 items are missing then the total score will be set to missing.

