#### 12.6.3.2.4 Minnesota Nicotine Withdrawal Questionnaire

The MNWS will be administered daily from Days 0 to 6, and Days 31, 61 and 91 for the assessment of Day-1 to Day 5, and Days 30, 60 and 90 as it is a 24-hour recall questionnaire.

All summaries, profiles and analysis will be presented for the THS 2.2 Menthol, mCC and SA arms.

The total score, along with the percent change from baseline will be summarized. The answers to the individual questions, along with the total score, the changes and percent changes from baseline will be listed.

The profiles of the raw means from baseline to Day 90 for the total scores will be plotted.

The analysis will compare each post baseline timpoint separately for the total score. An ANCOVA model will be used with terms for baseline score, sex, average daily mCC consumption over the last 4 weeks as reported during screening, and randomization arm,. No adjustment will be made for multiple comparisons.

The SAS code to be used is similar to the model reported in Section 12.6.1.3 "Sensitivity Analysis".

LS means for each product along with the difference (THS 2.2 Menthol - mCC) and (THS 2.2 Menthol – SA) with 95% CI will be presented in the tables.

All figures, summaries and analyses will be performed on the PP Set and FAS only.

The data will be presented in the below outputs:

TFL number	Title
FIGURES	
15.1.2.8.1	MNWS Total Score Arithmetic Mean and 95% CI – PP Set
15.1.2.8.2	MNWS Total Score Arithmetic Mean and 95% CI – FAS
15.1.2.9.1	MNWS Total Score Arithmetic Least Squares Means and 95% CI – PP Set
15.1.2.9.2	MNWS Total Score Arithmetic Least Squares Means and 95% CI – FAS
TABLES	
15.2.4.56.1	Descriptive Statistics of MNWS Total Score – PP Set
15.2.4.56.2	Descriptive Statistics of MNWS Total Score – FAS
15.2.4.57.1	Analysis of MNWS Total Score – PP Set
15.2.4.57.2	Analysis of MNWS Total Score – FAS
LISTINGS	
15.3.6.15	Listing of MNWS Questionnaire Results and Changes from Baseline

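### For the MNWS total score, using 1 as the denominator at a zero baseline gives a scale-dependent, non-monotone percent change; absolute change should be summarized instead

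*SAP*

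**What the plan says.** SAP Section 7 defines percent change as follow-up minus baseline, divided by baseline, times 100. For the arm summary it states: "Mean percent change from baseline is the mean of all individual subjects’ percent change from baseline values". For a zero denominator it adds: "When the baseline value is 0, 1 will be used in the denominator for calculating the percent change from baseline". The rule is general and not tied to any one variable.

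SAP Section 7.3.5 describes the MNWS items as ones "which are rated over the last 24 hours on a scale of 0 to 4", and then: "The total scores will be derived by calculating the average of all the non-missing data from the first 9 items". The total is set to missing only if more than half of those nine items are missing.

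SAP Section 12.6.3.2.4 gives the descriptive output: "The total score, along with the percent change from baseline will be summarized". Absolute changes are derived as well, but are assigned to the listing. The comparison between arms is a model of the score itself: "An ANCOVA model will be used with terms for baseline score, sex, average daily mCC", with the text going on to consumption over the last four weeks and randomization arm.

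For the FTND, Section 7.3.2 has its own version of the substitution, placed after Table 4: "If the baseline score is 0, the percent change from baseline will be calculated using a value of 1 for the denominator". That score is an integer total: "The FTND total score will be derived by summing the individual item scores if all items are non-missing". The FTND analysis section, 12.6.3.2.1, presents the score, the dependence categories, the absolute change from Screening and a shift table. It includes no percent change.

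**The concern.** A constant put in place of a zero denominator is harmless only if it is sensible on the scale of the variable. On the MNWS average scale, 1 is nine times the smallest non-zero score. A subject without symptoms at baseline is therefore treated as if the starting level were moderate, while a subject with one item rated 1 is divided by 1/9. Two subjects with almost the same course receive very different percent changes, and the one who worsened more gets the smaller figure.

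Such baselines are plausible. The MNWS is a 24-hour recall, and the baseline assessment precedes the first use of the randomized product (SAP 12.1.4), when all subjects had been smoking freely. That is an inference, because neither document gives a distribution of baseline scores. At stake is the readability of the arm means of percent change in the MNWS descriptive tables.

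**Working it through.** **Inputs.** Item range 0 to 4 and averaging over nine items (SAP 7.3.5); percent-change formula, zero rule and averaging across subjects (SAP 7); FTND integer sum, 0 to 10 (SAP 7.3.2); planned arms of 80, 40 and 40 (SAP Table 1). The plan states no figure of its own for this rule, so there is none to reproduce.

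**Formula.** Percent change = 100 × (f − b)/b for baseline b > 0, and 100 × (f − 0)/1 for b = 0.

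**MNWS, follow-up f = 1.0, all nine items answered.**

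| Baseline | Percent change | Absolute change |
|---|---|---|
| 0 | 100 × (1 − 0)/1 = +100% | +1.00 |
| 1/9 | 100 × (1 − 1/9)/(1/9) = +800% | +0.89 |
| 2/9 | 100 × (1 − 2/9)/(2/9) = +350% | +0.78 |

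Absolute change falls steadily as baseline rises. Percent change jumps up between 0 and 1/9 and then falls. The zero-baseline subject gets the same value as one starting at 0.5, since 100 × (1 − 0.5)/0.5 = +100%.

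**Other follow-up scores, baseline 0 against 1/9.** f = 2/9: +22% against +100%. f = 2.0: +200% against +1700%. f = 4.0: +400% against +3500%.

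**Missing items.** With k items answered, the smallest non-zero score is 1/k. For f = 1.0 it gives 100 × (k − 1)%, which is +400% to +700% for k = 5 to 8.

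**Dependence on scale.** Score the same nine items as a sum (0 to 36). A follow-up average of 1.0 becomes 9. Baseline 0 now gives 100 × 9/1 = +900%, while a baseline sum of 1 still gives 100 × (9 − 1)/1 = +800%. Only the substituted value changes with the scoring convention.

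**Weight in an arm mean.** With every planned subject contributing, one subject going from 1/9 to 1.0 adds 800/80 = 10 points in an arm of 80 and 800/40 = 20 points in an arm of 40. One going from 0 to 1.0 adds 100/80 = 1.25 and 100/40 = 2.5 points.

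**FTND.** The smallest non-zero score is 1, so follow-up f gives 100f% from baseline 0 and 100(f − 1)% from baseline 1. The gap is always 100 points, with the zero baseline giving the larger value. The MNWS pattern cannot arise here.

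**The case against.** The strongest reply has four parts.

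- **The large values do not come from the substitution.** They come from dividing by a small non-zero baseline. Deleting the rule would leave +800% and +350% as they are and would drop symptom-free subjects from the percent-change summary. This is right. It means that leaving percent change undefined at 0 is not enough alone, and that moving to absolute change is the main remedy.
- **Interpretable MNWS output already exists.** Section 12.6.3.2.4 summarizes the score itself, plots raw mean profiles, and reports baseline-adjusted least squares mean differences with confidence intervals. Section 12.1.3 requires medians and quartiles, which resist a few extreme values. This also stands, and it keeps the point minor.
- **Frequency is unknown.** The substitution acts only when every answered item among the first nine is 0, and those items include craving to smoke. The documents give no count. QSU-brief and MCEQ items start at 1, so those scores cannot be 0. This stands.
- **FTND is not affected in practice.** No percent change is among its outputs, and the absolute change is already planned. This stands. What remains is an unused definition.

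A reader might infer that the rule makes both the MNWS and the FTND percent changes meaningless, or that it biases the comparison of THS 2.2 Menthol with smoking abstinence on withdrawal. The documents do not support either. The FTND percent change is never tabulated. The MNWS comparison with abstinence uses scores rather than percent changes, and the SAP also compares those two arms on biomarkers of exposure, CYP1A2, risk markers and the QSU-brief.

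**Conclusion.** The point holds for the MNWS descriptive summary only. There the zero-baseline rule yields a percent change that is not monotone in baseline and depends on whether items are averaged or summed, and small non-zero baselines inflate the same column by the ordinary formula. At a follow-up of 1.0 the spread is +100%, +800% and +350% for baselines that differ by at most 2/9 of a scale point. These figures assume all nine items answered. How far an arm mean would move depends on how many subjects start at or near 0, which the documents do not give.

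The MNWS is exploratory. No test, estimated arm difference or success criterion uses its percent change, so this is an optional improvement. For the FTND the finding is only that Sections 7.3.2 and 12.6.3.2.1 do not match.

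**What to change.** Three wording changes in the SAP:

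1. In Section 12.6.3.2.4, summarize absolute change from baseline in the MNWS total score in place of percent change.
2. In Section 7, leave percent change undefined when the baseline is 0, and drop the substitution of 1.
3. In Section 7.3.2, delete the FTND percent-change sentence, so that it agrees with Section 12.6.3.2.1.

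The cost is text and one table shell. No new data are needed, since absolute MNWS changes are already derived for the listing. If percent change is kept in that listing, a footnote should say that it is not calculated at a zero baseline.

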### 7.1 Biomarkers

#### 7.1.1 Biomarkers of Exposure and Risk Markers in Urine

The adjustment of the urinary BoExp and Risk Markers concentration for creatinine will be calculated as:

$$\text{Biomarker (corrected for creatinine)} = \frac{\text{Biomarker]}{\text{Creatinine]}}$$

where the [ ] indicated concentrations measured from the same 24 hour urine collection or 4-hour urine fraction.

The quantity excreted for a BoExp over 24 hours will be calculated as:

$$\text{Quantity Excreted over 24 hours} = \text{Biomarker} * \text{urine volume}$$

where the concentration and the urine volume are from the same 24 hour urine collection.

### 7.1.2 Nicotine Equivalents

The quantity excreted of NEQ in 24 hours will be derived according to the formula below. The concentrations reported for free nicotine and its five major metabolites will not be used as analysis variables.

$$\text{NEQ [g]} = (\text{free nicotine}_c [\mu\text{mol/l}] + \text{nicotine-glucuronide}_c [\mu\text{mol/l}] + \text{free cotinine}_c [\mu\text{mol/l}] + \text{cotinine-glucuronide}_c [\mu\text{mol/l}] + \text{free trans-3'-hydroxycotinine}_c [\mu\text{mol/l}] + \text{trans-3'-hydroxycotinine-glucuronide}_c [\mu\text{mol/l}]) * 162.2[\mu\text{g}/\mu\text{mol}] * \text{urine volume (l)} / 1000 [\mu\text{g}/\text{mg}]$$

N.B. All concentrations must be in  $\mu\text{mol/l}$  before applying the above formula.

The conversion factors will be applied as follows:

Free nicotine	The molecular weight is 162.232 g/mol ( Chemical Information Specialized Information Services RN:54-11-5 ). Therefore to convert nicotine from ng/mL to nmol/L, the result in ng/mL is multiplied by 6.164.
Nicotine glucuronide	The molecular weight is 338.356 g/mol ( Chemical Information Specialized Information Services RN:152306-59-7 ). Therefore to convert nicotine from ng/mL to nmol/L, the result in ng/mL is multiplied by 2.955.
Cotinine	The molecular weight is 176.218 g/mol ( Chemical Information Specialized Information Services RN:486-56-6 ). Therefore to transform cotinine from ng/mL to nmol/L, the result in ng/mL will be multiplied by 5.675.
Cotinine-glucuronide	The molecular weight is 352.341 g/mol ( Chemical Information Specialized Information Services RN:139427-57-9 ). Therefore to transform cotinine from ng/mL to nmol/L, the result in ng/mL will be multiplied by 2.838.
Trans-3'-hydroxycotinine	The molecular weight is 192.217 g/mol ( Chemical Information Specialized Information Services RN:34834-67-8 ). Therefore to transform trans-3' hydroxycotinine from ng/mL to nmol/L, the result in ng/mL is multiplied by 5.202.

Trans-3'hydroxycotinine-glucuronide

The molecular weight is 368.34g/mol (**Chemical Information Specialized Information Services RN:132929-88-5**). Therefore to transform trans-3' hydroxycotinine from ng/mL to nmol/L, the result in ng/mL is multiplied by 2.715.

The adjustment of NEQ for creatinine in urine will be calculated as:

$$\text{NEQ (corrected for creatinine)} = \frac{\text{NEQ}]}{\text{Creatinine}]}$$

where the concentrations are measured from the same 24 hour urine collection or 4-hour urine fraction.

### 7.1.3 CYP1A2

CYP1A2 activity is calculated as the molar metabolic ratio of PX / CAF in plasma, both expressed in molar equivalent (nmol/L).

The conversion factor will be applied as follows:

PX

The molecular weight is 180.166 g/mol (**Chemical Information Specialized Information Services RN:611-59-6**). Therefore to convert PX in ng/mL to nmol/L the result in ng/mL is multiplied by 5.550.

CAF

The molecular weight is 194.193 g/mol. (**Chemical Information Specialized Information Services RN:58-08-2**). Therefore to convert CAF in ng/mL to nmol/L the result in ng/mL is multiplied by 5.150.

The converted results will be calculated to three decimal places and the ratio will be reported as a percentage with two decimal places.

If either of the PX or CAF concentration is LLOQ then the ratio will not be calculated.

### 7.1.4 CYP2A6

CYP2A6 activity is calculated in plasma as the metabolic ratio of trans-3' hydroxycotinine and cotinine, both expressed in molar equivalent (nmol/L) (**Jacob et al. 2011**).

The conversion factor will be applied as follows:

Cotinine	The molecular weight is 176.215 g/mol ( Chemical Information Specialized Information Services RN:486-56-6 ). Therefore to transform cotinine from ng/mL to nmol/L, the result in ng/mL will be multiplied by 5.675.
Trans-3'hydroxycotinine	The molecular weight is 192.217 g/mol ( Chemical Information Specialized Information Services RN:34834-67-8 ). Therefore to transform trans-3' hydroxycotinine from ng/mL to nmol/L, the result in ng/mL is multiplied by 5.202.

The converted results will be calculated to three decimal places and the ratio will be reported as a percentage with two decimal places.

If either of the cotinine or trans-3'hydroxycotinine concentration is LLOQ then the ratio will not be calculated.

## 7.2 Pharmacokinetic Parameters

The peak nicotine and cotinine plasma concentration ( $C_{peak}$ ) and time to peak concentration ( $t_{peak}$ ) will be obtained directly from the concentrations taken on Day 5. If the peak concentration occurs at more than one time point then  $t_{peak}$  will be assigned to the first value. The weighted average concentration over 24 hours on Day 5 ( $C_{avg}$ ) will be calculated by dividing the area under the curve from 0 to 24 h ( $AUC_{0-24\ h}$ ) by 24, where the  $AUC_{0-24\ h}$  is calculated using the linear trapezoidal rule.

Since the samples are taken whilst the subjects are smoking freely all samples must be non-missing for the parameters to be calculated as  $C_{peak}$  (and  $t_{peak}$ ) could occur at any time.

## 7.3 Questionnaires

### 7.3.1 Socio-Economic Status Questionnaire

On Day 4, subjects will be asked a series of questions related to their education, occupational status, size and annual income of their household. These data will be used to create a measure for Socio-Economic Status (SES) that categorizes subjects into low, moderate and high SES for educational attainment, annual household income and a composite measure for educational attainment and income as detailed in **Table 3** below (**King et al., 2011**).

**Table 3: Classification for the Socio-Economic Status Questionnaire**

Category	Classification	Item
Question 1. What is the highest level of education you have completed?	Low	1 (Less than high school) 2 (high school graduate) 3-5 (some college, college graduate, advanced degree)
Question 2. What is your current occupational status?	Moderate	Working now Only temporarily laid off, sick leave or maternity leave Looking for work, unemployed Retired Disabled, permanently or temporarily Keeping house Student Other
Question 3. How many people are currently living in your household?	High	Not applicable
Question 4. Of these people how many are children?	Low	Not applicable
Question 5. Of these people how many are adults?	Moderate	Not applicable
Question 6. Of the adults, how many bring income into the household?	High	Not applicable
Question 7. Which of these categories best describes your total combined family income for the past 12 months? This should include income (before taxes) from all sources, wages, rent from properties, social security, disability and/or veteran's benefits, unemployment benefits, workman's compensation, help from relatives (including child payments and alimony), and so on.	Low	1-2 (Less than \$10,000 or \$10,000 to \$29,999) 3-4 (\$30,000 through \$44,999 or \$45,000 through \$59,999) 5-8 (\$60,000 through \$74,999 or \$75,000 through \$99,999 or \$100,000 through \$149,999 or \$150,000 and over)

Educational attainment will be classified as follows: if multiple answers are obtained the higher degree will be chosen; the subject cannot be classified if the answer is missing. Annual household income will be classified as follows: if multiple answers are obtained then the higher income will be chosen; the subject cannot be classified if the answer is missing or if option 9 or 10 is selected.

Education and income categories will be combined to create a composite measure for SES with the following tertile division:

- Low            Low education and Low income categories
- Moderate    Low income and Moderate education, Low income and High education, Moderate income and Low education, and High income and Low education
- High           Moderate income and Moderate education, Moderate income and High education, High income and Moderate education, and High income and High education)

Respondents who do not report either income or education will be excluded from the analysis of the composite SES.

### 7.3.2 Fagerström Test for Nicotine Dependence (FTND)

The FTND will be used in its revised version (**Heatherton et al 1991**), as updated in 2012 (**Fagerström et al. 2012**). These questions are to be answered by the subject themselves. It is conducted at Screening to determine subject's dependence on nicotine and on the Day 90 Visit to assess any changes in their dependence on nicotine.

**Table 4** describes the six questions the questionnaire consists of, and the scores associated with each question.

The FTND total score will be derived by summing the individual item scores if all items are non-missing, otherwise the total score will be set to missing. For the FTND total score, descriptive statistics and frequency tables according to the following classification will be provided (**Fagerström et al. 2012**):

Mild	0 – 3
Moderate	4 – 6
Severe	7 – 10

**Table 4: Scoring for the Fagerstrom Test for Nicotine Dependence**

FTND Question	Response	Score
1 How soon after you wake up do you smoke your first cigarette?	Within 5 minutes	3
	6 to 30 minutes	2
	31 to 60 minutes	1
	After 60 minutes	0

